**REFERENCES:** See References section**Objectives**

Two common corticosteroids used for trigger finger treatment are betamethasone and methylprednisolone. Both injections are effective in treating trigger finger and the decision of which to use in treatment is currently a matter of the current practice and physician preference. There is no literature comparing the side effects, specifically flare reactions between these two treatments. Our goal through this randomized trial is to see whether there is a difference between these two corticosteroids in inducing flare reactions and if there are any differences in the peak level of pain and their duration.

Findings indicating a statistically significant difference in the incidence and/or intensity of the flare reactions would be clinically significant and would be evidence supporting the switch of current practice to one corticosteroid over the other.

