## OFFICE OF HUMAN RESEARCH PROTECTION

**Study Design** – The two standard of care corticosteroids used for trigger finger treatment are betamethasone and methylprednisolone. Both injections are effective in treating trigger finger and the decision of which to use in treatment is currently a matter of the current practice and physician preference. There is no literature comparing the side effects, specifically flare reactions between these two treatments. Our goal through this randomized trial is to see whether there is a difference between these two corticosteroids in inducing flare reactions and if there are any differences in the peak level of pain and its duration. We will carry out a double-blinded randomized trial enrolling patients into one of the two treatment groups. The volume of the doses of steroid to be given will be standardized to 1 cc of either methylprednisolone (40 mg) or betamethasone (6 mg). We will instruct patients who meet the inclusion criteria to complete a visual analog scale (VAS) of their pain (1-10) prior to the injection, immediately after the injection, five minutes after the injection, and once a day for a minimum of 7 days after the injection. The incidence, intensity, time to peak and time to resolution of the flare reactions (defined as a 2-point increase from pre-injection pain) will be assessed and compared between the two groups. Findings indicating a statistically significant difference in the incidence and/or intensity of the flare reactions would be clinically significant and would be evidence supporting the switch of current standard practice to one corticosteroid over the other. Patients will only receive a single, standard of care, trigger finger injection on the day they present to the clinic. The next 7 days, up to two weeks if needed, of follow-up will only be a single short survey question to determine pain level.

Patients will be identified by the surgeon on the day they present to clinic, and will be recruited and consented by the study personnel. Data will be collected from the patient and stored in the REDCap server. There is not more than minimal risk involved.

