## Section II: Design

### Background & Significance

Corticosteroid injections are effective non-surgical approach to treating trigger finger (stenosing tenosynovitis) with success rates reported as high as 92% after just one injection [1]. Among their side effects is a post-injection flare of increased pain that is attributed to crystal-induced synovitis [2]. Reports of these flares in the literature have been rare. Recent evidence their incidence can be as high as 33% [3]. We feel they are a more common clinical issue than traditionally reported and it would be beneficial to control and reduce their incidence if possible.

Two common corticosteroids used for trigger finger treatment are betamethasone and methylprednisolone [4][5]. Both injections are effective in treating trigger finger and the decision of which to use in treatment is currently a matter of the current practice and physician preference. There is no literature comparing the side effects, specifically flare reactions between these two treatments. Our goal through this randomized trial is to see whether there is a difference between

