## OFFICE OF HUMAN RESEARCH PROTECTION

these two corticosteroids in inducing flare reactions and if there are any differences in the peak level of pain and their duration.

We will carry out a double-blinded randomized trial enrolling patients into one of the two treatment groups. The volume of the doses will be standardized to 1 cc of either methylprednisolone (40 mg) or betamethasone (6 mg). We will instruct patients who meet the inclusion criteria to complete a visual analog scale (VAS) of their pain (1-10) prior to the injection, during the injection and once a day for the following 7 days after the injection. We estimate that we need a minimum of 30 patients in each group to achieve a minimum of 80% power and 0.05 significance. The incidence, intensity, time to peak and time to resolution of the flare reactions (defined as a 2-point increase from pre-injection pain [3]) will be assessed and compared between the two groups. Findings indicating a statistically significant difference in the incidence and/or intensity of the flare reactions would be clinically significant and would be evidence supporting the switch of current practice to one corticosteroid over the other.

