**Study Design & Methodology**

The two standard of care corticosteroids used for trigger finger treatment are betamethasone and methylprednisolone. Both injections are effective in treating trigger finger and the decision of which to use in treatment is currently a matter of the current practice and physician preference. There is no literature comparing the side effects, specifically flare reactions between these two treatments. Our goal through this randomized trial is to see whether there is a difference between these two corticosteroids in inducing flare reactions and if there are any differences in the peak level of pain and its duration. We will carry out a double-blinded randomized trial enrolling patients into one of the two treatment groups. The volume of the doses of steroid to be given will be standardized to 1 cc of either methylprednisolone (40 mg) or betamethasone (6 mg). We will instruct patients who meet the inclusion criteria to complete a visual analog scale (VAS) of their pain (1-10) prior to the injection, immediately after the injection, five minutes after the injection, and once a day for a minimum of 7 days after the injection. The incidence, intensity, time to peak and time to resolution of the flare

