### Target Population & Recruitment Methods

We will recruit a minimum of 30-40 patients into each treatment group. Power analysis shows that at least 30 patients are needed to show a difference of 2-point difference between the two groups which corresponds to the minimal clinically important difference on the VAS scale assuming a standard deviation of 2.5 points. Accounting for the potential of patient data loss during follow-up surveys, we expect to need to consent and enroll 80-100 patients

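### The plan equates a significant difference in flare incidence or intensity with clinical importance and sets no size of effect; for intensity this conflicts with its own 2-point threshold, and no primary outcome is named

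*Combined protocol and SAP*

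**What the plan says.** The key sentence stands in four places: Study Design in the Research Summary, Background & Significance, Objectives, and Study Design & Methodology. Under Objectives it says that a "statistically significant difference in the incidence and/or intensity of the flare reactions would be clinically significant" and that such a finding "would be evidence supporting the switch of current practice to one corticosteroid over the other". The Research Summary version ends almost identically: "would be evidence supporting the switch of current standard practice to one corticosteroid over the other". None of the four gives a size of effect.

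Target Population & Recruitment Methods bases the sample size on a 2-point difference between groups, "which corresponds to the minimal clinically important difference on the VAS scale assuming a standard deviation of 2.5 points". The Statistical Analysis Plan repeats this basis. The Statistical Analysis Plan then lists four comparisons (incidence, intensity, time to flare and time to resolution), to be made by t-test or chi-square test. It names no primary outcome, no order of testing and no adjustment. The only significance level is in Background & Significance, where at least 30 patients per group are needed "to achieve a minimum of 80% power and 0.05 significance".

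On numbers, "We will recruit a minimum of 30-40 patients into each treatment group", with 80-100 enrolled in total to allow for lost follow-up data. A flare is a rise of 2 points from the patient's own pre-injection score. No section says what between-group difference in flare incidence would matter.

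**The concern.** For intensity the plan holds two standards of clinical importance. One is a 2-point difference between groups. The other is any difference that reaches significance. They disagree whenever a difference is significant but smaller than 2 points, and the repeated sentence would then label that result clinically significant and count it in favour of a switch.

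For incidence there is no threshold to contradict. The 2-point rise in the flare definition is a change within a patient and does not say how many fewer flares would matter.

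The and/or wording also lets either of two tests support the conclusion, with no statement of how error is controlled across them. At stake is whether a small or chance difference is reported as grounds for changing practice.

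**Working it through.** **Inputs.** From the plan: SD 2.5, threshold 2 points, level 0.05, power at least 80%, at least 30 per group with 30-40 recruited, 80-100 enrolled, flare incidence as high as 33% (Background & Significance). Assumed, because not stated: two-sided tests and equal allocation. Fifty per group would need maximum enrolment, equal allocation and no data loss.

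**1. The plan's own figure.** n per group = 2 × (1.960 + 0.842)² × 2.5² / 2² = 24.5, so 25; the exact t-test gives 26. At 30 per group the t-test has 86.1% power. Thirty is therefore more than the inputs require and consistent with a minimum of 80%.

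**2. Smallest significant difference, intensity compared in all patients.** Difference = t(0.975, 2n−2) × 2.5 × √(2/n). Its 95% CI runs from 0 to twice that value.

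| n per group | t | SE | Smallest significant difference | Upper 95% limit |
|---|---|---|---|---|
| 30 | 2.002 | 0.645 | 1.29 | 2.58 |
| 40 | 1.991 | 0.559 | 1.11 | 2.23 |
| 50 | 1.984 | 0.500 | 0.99 | 1.98 |

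**3. A true difference of 1 point, all patients.** The probability of significance comes from the noncentral t with d = 1/2.5 = 0.4. It is 33% at 30, 42% at 40 and 51% at 50 per group. The probability that the estimate reaches 2 points is 1 − Φ((2 − 1)/SE), or 6%, 4% and 2%. Those three figures are over all trials. Among significant trials only they become about 18%, 9% and 4% (for example 6.1/33.2 = 18%).

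**4. Intensity compared only in patients with a flare.** At 33% flares there are about 10, 13 and 16 such patients per group when n is 30, 40 and 50. With SD 2.5 the formula in step 2 gives 2.35, 2.02 and 1.81 points. The SD among flare patients may well be smaller. If the change is normal with SD 2.5 and only the upper 33% is kept, the SD is about 1.3 and the thresholds are about 1.24, 1.07 and 0.95. The plan says neither which patients are compared nor what SD applies to them.

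**5. Either-test false positives when neither outcome differs.**
- Two independent tests at 0.05: 1 − 0.95² = 9.75%. With bivariate normal test statistics: 9.1% at correlation 0.5 and 7.0% at 0.9.
- Simulation with a single normal change score (SD 2.5, flare = rise of at least 2, flare rates 10%, 20% and 33%, 30 to 50 per group, chi-square with and without correction, intensity in all or in flare patients): 5.7% to 10.3%. The 10% and 20% rates are assumptions.
- Simulation of the peak of seven correlated daily readings on a bounded 1-10 scale, all patients: 5.8% to 9.4%. It assumes baseline mean 5, SD 2.5 and within-patient correlation 0.5 or 0.8. It leaves out the immediate and five-minute readings and any follow-up beyond seven days.

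The excess over 5% is modest. It depends on the model, on the chi-square version and on which patients enter the intensity comparison.

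**The case against.** The best defence is that the sentence is rationale and not a decision rule. It speaks of evidence in support of a switch, and it is absent from the Statistical Analysis Plan, which itself cites the 2-point threshold. A sample size built on a VAS difference also suggests that intensity is the main outcome. Part of this stands: the sentence is loosely worded and intensity is the implied choice. But the sentence is made four times, once under Objectives, and it is the only statement of how a result becomes a recommendation. Nothing labels intensity primary, and the Background gives incidence as the motive: "it would be beneficial to control and reduce their incidence if possible".

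Several stronger readings are tempting, and the documents do not support them:

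- **That significance always arrives below 2 points.** This holds for an all-patient comparison at SD 2.5. In flare patients only, at 33% flares and the same SD, the threshold is above 2 at 30 and 40 per group. The missing size criterion remains either way.
- **That a barely significant result rules out 2 points.** The whole interval lies below 2 only at 50 analysed per group. At 30 and 40 it reaches 2.58 and 2.23.
- **That the either-or rule doubles the error rate.** Nearly 10% is the top of a model-dependent range that starts near 6%.
- **That a switch of practice is the trial's stated purpose.** The stated goal is to see whether the two steroids differ in flares, peak pain and duration. The switch is presented as a consequence.

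**Conclusion.** The concern holds as a conflict of wording with practical effect. As written, the plan would call a significant intensity difference clinically important whatever its size, against its own 2-point threshold. For incidence it would do so with no threshold at all. That reading of the text is secure.

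The numbers are conditional. The 1.29 and 1.11 points at 30 and 40 per group, and the 33% and 42% chance of labelling a true 1-point difference clinically significant, assume intensity is compared in all patients, SD 2.5, two-sided 0.05 and equal groups. The values at 50 per group (0.99 points and 51%) are an upper extreme. The multiplicity point is secondary, and the wording conflict stands without it. The trial's design is not undermined. The rule for interpreting it should be corrected.

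**What to change.** **In the four places where the sentence appears,** remove the claim of clinical significance and substitute wording such as: *Statistical significance alone will not be taken as clinical importance or as support for a switch. The difference in intensity, compared in all randomized patients with data, will be reported with its 95% CI and interpreted against 2 points. The risk difference in flare incidence will be reported with its 95% CI.* Intensity should be compared in all randomized patients with data because flare patients are a subset formed after randomization.

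**In the Statistical Analysis Plan,** name one primary outcome at two-sided 0.05, chosen by the sponsor before the data are analysed, and make the others secondary. One primary outcome is enough. Splitting the error between two outcomes is not needed, and testing at 0.025 (the lower bound under a Holm procedure) would put power for 2 points at 30 per group at 78.5%, below the stated 80%.

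**Cost.** These are text edits, with no change to enrolment or visits. The outcome not chosen loses confirmatory status, which matters if that is incidence. A significant difference below 2 points no longer supports a switch by itself. The stated 80% power at 30 per group still holds for a 2-point VAS difference, but it does not cover incidence. If incidence is chosen, for an assumed 33% against 10% at 30 per group, exact power is 59.9% with the uncorrected chi-square and 47.6% with the corrected one. The sample-size statement would then need its own justification.

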**Study Design & Methodology**

The two standard of care corticosteroids used for trigger finger treatment are betamethasone and methylprednisolone. Both injections are effective in treating trigger finger and the decision of which to use in treatment is currently a matter of the current practice and physician preference. There is no literature comparing the side effects, specifically flare reactions between these two treatments. Our goal through this randomized trial is to see whether there is a difference between these two corticosteroids in inducing flare reactions and if there are any differences in the peak level of pain and its duration. We will carry out a double-blinded randomized trial enrolling patients into one of the two treatment groups. The volume of the doses of steroid to be given will be standardized to 1 cc of either methylprednisolone (40 mg) or betamethasone (6 mg). We will instruct patients who meet the inclusion criteria to complete a visual analog scale (VAS) of their pain (1-10) prior to the injection, immediately after the injection, five minutes after the injection, and once a day for a minimum of 7 days after the injection. The incidence, intensity, time to peak and time to resolution of the flare

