## OFFICE OF HUMAN RESEARCH PROTECTION

reactions (defined as a 2-point increase from pre-injection pain) will be assessed and compared between the two groups. Findings indicating a statistically significant difference in the incidence and/or intensity of the flare reactions would be clinically significant and would be evidence supporting the switch of current standard practice to one corticosteroid over the other. Patients will only receive a single, standard of care, trigger finger injection on the day they present to the clinic. The next 7 days, up to two weeks if needed, of follow-up will only be a single short survey question to determine pain level.

All survey data will be collected from the patient in real-time, but the study will include a retrospective chart review to collect demographic information, injection specifics, etc.

Data to be collected: information from your existing medical records, and new information about you that is created or collected during this study, such as: history and physical information pertaining to trigger finger, nursing and staff notes pertaining to trigger finger, identifiers (name, MRN), demographic data (age/date of birth, sex, dominant hand), patient reported outcome measures scores, comorbidities (tobacco use, diabetes, fibromyalgia).

This study does not involve more than minimal risk. Risks from participation in this study include typical risks associated with a trigger finger injection: pain at injection site, soreness, etc.

The subject will receive no direct benefits. Knowledge gained from this study could help change standard of care procedures for trigger finger injections to best limit flare reactions afterward.

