#### ***Inclusion & Exclusion Criteria –***

***Inclusion:*** Adult, Single trigger injection, First time for the digit to be injected, No prior surgery on digit  
***Exclusion:*** Current oral steroid use, Rheumatoid arthritis, More than one single digit involved, Previous injection in same digit, Prior surgery on same digit, Other injections in the same clinic on the same day, Under 18, Cognitively impaired individuals, Pregnant women, Prisoners, WVU/WHUH/UHA Employees or students

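### The pain scale is written as 1-10 with no value for absence of pain, so whether a 2-point rise in a pain-free patient counts as a flare depends on an anchor that the plan does not state

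*Combined protocol and SAP*

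**What the plan says.** The scale is described three times: under Study Design in the Research Summary, in Background & Significance, and in Study Design & Methodology. The last has patients "complete a visual analog scale (VAS) of their pain (1-10) prior to the injection, immediately after the injection, five minutes after the injection", followed by daily ratings. Background & Significance lists different clinic time points but the same range: "visual analog scale (VAS) of their pain (1-10) prior to the injection, during the injection and once a day for the following 7 days". No section gives a 0-10 range, words for either end of the scale, or a rule for recording absence of pain.

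A flare is "defined as a 2-point increase from pre-injection pain". Incidence, intensity, time to peak and time to resolution of flares are all derived from this one pain rating. The Objectives treat a significant difference in incidence and/or intensity as grounds for changing practice.

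The inclusion criteria are "Adult, Single trigger injection, First time for the digit to be injected, No prior surgery on digit". Neither they nor the exclusions mention pain, so patients need neither a minimum pain score nor freedom from pain.

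**The concern.** A change-from-baseline rule needs a defined lower end of the scale. Here the lowest permitted score is 1, and nothing tells the patient whether 1 means no pain or slight pain. A patient whose finger triggers without pain on the day has no score that clearly describes that state.

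If such patients enter 1 and otherwise rate as they would on a 0-10 scale, the flare rule asks more of them. With whole-number ratings they need a true rise of 3 points, where everyone else needs 2. Any later pain in these patients is also recorded as a rise that is 1 point too small, which is half of the 2-point minimal clinically important difference in the Statistical Analysis Plan. The smallest qualifying flares would be missed, and a real difference between arms in such flares would be diluted.

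**Working it through.** **Inputs from the documents.** Scale 1-10; flare = rise of at least 2 from the pre-injection score; flare incidence up to 33% (Background & Significance); difference 2 points and SD 2.5 (Statistical Analysis Plan); at least 30 per group. The documents do not give mean baseline pain, the share of pain-free patients, or the reading-to-reading SD. These are assumed below.

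**The plan's own figure.** The normal formula gives n = 2 × (1.96 + 0.84)² × 2.5² / 2² = 24.5, so 25 per group (26 by the exact t-test). At 30 per group power is about 0.86 to 0.87, so the stated minimum of 30 is conservative. This point does not depend on that figure, and the fix does not change it.

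**Step 1: score arithmetic.** Three ways in which a true 0-10 pain level could be entered on a 1-10 scale:

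| True rise | Only 0 is raised to 1 | All scores shift up by one | Linear rescaling, 1 + 0.9 × pain |
|---|---|---|---|
| 0 to 2 | 1 to 2: +1, no flare | 1 to 3: +2, flare | 1.0 to 2.8: +1.8, no flare; flare if rounded (1 to 3) |
| 0 to 3 | 1 to 3: +2, flare | 1 to 4: +3, flare | 1.0 to 3.7: +2.7, flare |
| 1 to 3 | 1 to 3: +2, flare | 2 to 4: +2, flare | 1.9 to 3.7: +1.8, no flare; flare if rounded (2 to 4) |

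In the first column only patients with baseline pain below 1 are affected. If 1 is the no-pain anchor, the scale is 9 points wide and a 2-point step is 2/9 = 22% of its range instead of 2/10 = 20%, which is negligible.

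**Step 2: size if only 0 is raised to 1.** Simulation of 200,000 patients per scenario. Assumptions: total SD 2.5; baseline mean 2, 3 or 4; seven daily whole-number ratings; 33% true flares lasting 2 days with a rise of 2, 3 or 4 points; underlying pain falling 50% over the week. The same random numbers were scored with a floor of 0 and a floor of 1.

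With reading SD 0.3 and flares of exactly 2 points:

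| Baseline mean | Rated 0 | Incidence, floor 0 | Incidence, floor 1 | Lost (percentage points) |
|---|---|---|---|---|
| 2 | about 26% | 26.6% | 19.4% | 7.2 |
| 3 | about 15% | 24.8% | 20.7% | 4.1 |
| 4 | about 8% | 22.8% | 20.8% | 2.0 |

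A hand check on the order of size is 0.33 × share rated 0, which gives 8.6, 5.0 and 2.6 points. The simulated losses are a little lower because rating noise carries some of these flares to a score of 3, which still counts. With rises of 3 or 4 points at SD 0.3 the loss is 0. Settings not fixed above move the absolute incidences by up to about 3 points, but the losses agree between runs.

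With reading SD 0.75, recorded incidence falls by about 1.4 to 7 points, but most of that fall is not true flares:

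| Scenario | Total fall | True flares lost | Noise-driven false flares removed |
|---|---|---|---|
| Mean 2, rise 2 | 7.0 | 3.2 | 3.8 |
| Mean 2, rise 3 | 4.2 | 0.4 | 3.8 |
| Mean 2, rise 4 | 3.8 | 0.0 | 3.8 |
| Mean 4, rise 3 or 4 | about 1.5 | at most 0.1 | the rest |

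True flares lost at this noise level are therefore 0 to 3.2 points.

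**Step 3: what attenuation could cost.** As an illustration only, take true rates of 33% against an assumed 10%, 30 per arm, and the same fraction of flares missed in both arms. Power is 59% with none missed, 53% with 10% missed and 47% with 20% missed. In the 33% arm, 10% and 20% missed correspond to 3.3 and 6.6 points.

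**The case against.** The strongest reply is that a 1-10 range does not say how patients map their pain onto it. On a scale that starts at 1, using 1 for no pain is at least as natural as treating it as slight pain, and then a 2-point rise is still recorded as 2 points. The range may also be shorthand for 0-10; the survey item itself is not in the documents. This stands. A reader might infer that every 0-to-2 rise is certain to be missed, but the text supports only that it may be.

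The size rests on borrowed inputs. The SD of 2.5 is given for the sample size and is not called the SD of baseline pain. The shares rated 0 come from clipping a normal curve at zero, and at mean 2 the clipped baseline SD is about 2.06. This also stands, so the figures are a range under assumptions and not an estimate for this trial.

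The reply does not remove the ambiguity. The same patient is a case or a non-case depending on an unstated anchor, and patients may use the scale differently from one another. If 0-10 was meant, the same edit settles the matter.

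**Conclusion.** The point holds as a minor, cheap improvement. The scale has no value or anchor for no pain, pain-free patients can enrol, and whether their 2-point rise counts as a flare is left to how each patient uses the scale. If only 0 is raised to 1, the smallest qualifying flares in patients with baseline pain below 1 are missed and their recorded rise is 1 point too small. Under the stated assumptions, true flares lost are 0 to about 7 percentage points. The top needs nearly noise-free ratings, flares of exactly 2 points and about 26% of patients rated 0. At reading SD 0.75 the loss is 0 to about 3 points. If scores shift up by one, nothing is lost.

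Three stronger readings are not supported. A reader might take the eligibility criteria to require freedom from pain; they are simply silent on it. A reader might take the whole fall in recorded incidence at the higher noise level as lost flares; much of it is false flares removed. And a reader might infer a bias toward one drug; the scale and the rule are the same in both randomised arms, so the expected effect is under-counting and possibly an attenuated difference.

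**What to change.** In Study Design (Research Summary), Background & Significance and Study Design & Methodology, replace the 1-10 range with a 0-10 scale anchored 0 = no pain and 10 = worst pain. Use the same range and anchors in every pre-injection, clinic and daily survey item, and in the REDCap field. Keep the 2-point flare definition.

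If patients have already been scored on 1-10, do not assign an anchor afterwards, because they may never have seen it. Report the wording they were shown, label those scores, and give flare incidence with and without patients whose pre-injection score was 1.

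The cost is a wording change in three places and in the survey fields, with no extra patients or visits and no change to the sample size. The one downside, if enrolment has begun, is that scores from before and after the change must be labelled and checked before they are pooled.
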